11.27. Pregnancy Test and Birth Control Record

An FDA approved rapid result urine pregnancy test will be used (i.e., dipstick test), unless the site IRB requires a blood-based assay. If applicable, subjects will be asked to sign a release of information form for study personnel to access medical records to obtain information regarding the outcome of a pregnancy that occurred during the study.

The Birth Control Assessment is designed to determine a female subject's compliance with the birth control specifications detailed in the inclusion criteria.

11.28. Prior and Concomitant Medications

All medications taken by the subject 2-months prior to the start of screening, during the screening period, and through the final follow-up contact will be recorded. All medications reported by the subject will be recorded on a source document and eCRF.

11.29. Physical Examination

A physical examination of the oral cavity, head, eyes, ears, nose, and throat, cardiovascular system, lungs, abdomen, extremities, skin, neuropsychiatric mental status and sensory/motor status, musculoskeletal system and general appearance will be performed during screening. The physical exam will be updated on the day planned for randomization by querying the subject about any physical changes since the screening examination. Weight (kg) will be collected per the schedule in Table 5. A symptom directed physical examination will be performed, as applicable, at other visits if the subject reports any problems. Abnormal findings will be reported as AEs, if appropriate.

11.30. Screen Failures Documentation

To document the reason that a subject who consented to the study was not randomized, the Enrollment and Eligibility Checklist eCRFs will be completed for these subjects.

11.31. Subject Disposition

A subject disposition eCRF will be completed for all subjects who are randomized to the study and who are dispensed investigational product. This eCRF will be used to record the following

data as applicable: 1) completion status of the subject at the end of their participation and if they were discontinued early, and reason for early discontinuation.

Completion status is as follows:

- 1. Subject completed full study (i.e., telephone contact was made at the Weeks 28 to 29 follow-up).
- 2. Subject completed the full intervention phase of the study (i.e., subject came to Week 27 clinic visit).
- 3. Subject was withdrawn prior to the Week 27 visit (reasons for early withdrawal are to be specified).
- 4. If the subject discontinued study medications.

Even if the subject had investigational product suspended for any reason but attended clinic visits, the above definitions still apply.

In addition, if the subject was confined and/or incarcerated at any time during the study, the dates of confinement and/or incarceration will be collected.

11.32. Drinking Goal

The Thoughts About Abstinence Scale developed by Marlatt et al (1988) for smoking was adapted for drinking and items for a drinking goal, and confidence and motivation to meet the selected goal have been included. The resultant assessment, named Drinking Goal, is a 3-item questionnaire completed by the subject and will be both the source and eCRF.

11.33. TLFB Interview

Drinking behavior will be assessed using the TLFB methodology (Sobell & Sobell-1992). The TLFB is a semi-structured interview that provides estimates of the daily quantity of alcohol consumption during specified time periods. It uses a calendar prompt and a number of other memory aids (e.g., holidays, payday, and other personally relevant dates) to facilitate accurate recall of drinking or other drug use during the target period. The procedure has been widely used in clinical and research contexts. It has demonstrated adequate levels of reliability and validity when administered as an in-person interview, over the telephone, and when administered via computer (Carey-1997, Sobell et al-1988, Sobell et al-1996). After consent is signed, the TLFB interview will be performed for the 28-day period prior to signing consent. Thereafter, the interview will be for the previous days between the last assessment and the day prior to the day of the assessment. It is estimated that a 28-day TLFB assessment will take 20 minutes to complete. In the event of missed visits, collection of missed drinking data at the following visit is required.

If a subject requests to withdraw from the study but agrees to continued telephone contact to assess drinking, the TLFB will be performed over the phone for the duration of the study at a frequency acceptable to the study subject and site staff.

An Excel spreadsheet customized for use in this study will be used for double data entry by clinical site staff to collect the TLFB drinking data. This spreadsheet contains a calculator to

determine standard drink units (SDUs). This spreadsheet will be reviewed, compared with source documents and collected by study monitors for upload into the main study database.

Drinking days are defined as the number of days in which the subject reported any alcohol consumption (i.e., > 0 standard drinking units [SDUs]). A standard drink contains approximately 0.6 fluid ounces (oz) of pure alcohol. The data given by the subjects on amount and type of alcoholic beverage(s) consumed will be converted to SDUs. Standard drink unit definitions are provided in Table 8.

Table 8: Standard Drink Unit Definitions

For Beer ($\sim 5\%$ alcohol), the approximate number of SDUs in:

- 12 oz = 1.0
- 16 oz = 1.3
- 22 oz = 2.0
- 40 oz = 3.3

For malt liquor (~ 7% alcohol), the approximate number of SDUs in:

- 12 oz = 1.4
- 16 oz = 1.9
- 22 oz = 2.6
- 40 oz = 4.7

For table wine (~ 12% alcohol), the approximate number of SDUs in:

- 750 mL bottle = 250z = 5.0
- 5 oz glass = 1.0
- 10 oz glass = 2.0

For 80 proof spirits (~ 40% alcohol), or hard liquor, the approximate number of SDUs in:

- 1.5 oz (mixed drink) = 1.0
- 16 oz (pint) = 11.0
- 25 oz (a fifth) = 17.0
- 1.75 L (59 oz) = 39.0

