9.1. Efficacy Endpoints

9.1.1. Primary Efficacy Endpoint

Self-reported daily alcohol consumption will be assessed using the TLFB method from 28 days before signing informed consent until the last study visit or contact. The primary efficacy endpoint examines the hypothesis that HORIZANT Extended-Release Tablets will increase the PSNHDD compared to placebo during the last 4 weeks of maintenance period of treatment (Study Weeks 22-25). A "heavy drinking day" is 4 or more drinks per drinking day for women and 5 or more drinks per drinking day for men. PSNHDD will also be analyzed during other time periods (i.e., the last 8, 12, 16, 20, and 24 weeks of the maintenance period) in exploratory analyses.

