11.34. World Health Organization Drinking Risk Categorical Scale

The WHO has developed a drinking risk categorical scale that can be used in a responder analysis approach to assess clinically relevant decreases in alcohol consumption (Aubin et al-2015). Two dichotomous endpoints will be analyzed: WHO 1-level and WHO 2-level decrease in alcohol consumption. The WHO 1- and 2-level decrease endpoints are the percentage of subjects experiencing at least 1- and 2-level decrease in WHO levels of alcohol consumption, respectively, from the level at baseline (the period including the 28 days before screening) to the level during the last 4 weeks of the maintenance phase (Study Weeks 22-25).

The WHO levels of average alcohol consumption per day are as follows:

	Males	Females
Low Risk	1 to 40g	1 to 20g
Medium Risk	41 to 60g	21 to 40g
High Risk	61 to 100g	41 to 60g
Very High Risk	101+g	61+g

where 14g = 1 SDU (WHO-2000). In computing the WHO alcohol consumption level, average drinks per day will be used, computed as the sum of all drinks in the 28 day period divided by the number of days with non-missing drinking data in that period. Abstinent subjects will be included in a separate "Abstinent" category. A subject must have at least 1 week of data during the last 4 weeks of the maintenance phase to be considered non-missing.

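### Table 8 counts 22 oz of 5% beer as 2.0 standard drinks, but the protocol's own definition gives 1.83; if the drinking calculator uses the table, some days below the heavy-drinking cut-off count as heavy

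*Protocol*

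**What the plan says.** Section 11.33 (TLFB Interview) fixes the size of a drink: "A standard drink contains approximately 0.6 fluid ounces (oz) of pure alcohol". Reported amounts and beverage types are to be converted to SDUs, and the section names Table 8 as the source of the SDU definitions. The conversion is done in a custom Excel spreadsheet with a built-in calculator, whose factors the protocol does not list.

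Table 8 heads its beer rows "For Beer ($\sim 5\%$ alcohol), the approximate number of SDUs in" and its malt liquor rows "For malt liquor (~ 7% alcohol), the approximate number of SDUs in". The beer rows are 12 oz = 1.0, 16 oz = 1.3, 22 oz = 2.0 and 40 oz = 3.3. The malt liquor rows are 1.4, 1.9, 2.6 and 4.7 for the same volumes. The large spirits containers are given as whole numbers: "16 oz (pint) = 11.0", "25 oz (a fifth) = 17.0" and "1.75 L (59 oz) = 39.0".

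Section 11.34 equates one SDU with 14 g. Section 9.1.1 sets a heavy drinking day at 4 or more drinks for women and 5 or more for men. The primary endpoint is the share of subjects with no such day in Weeks 22-25. Under section 12.4.2, missing drinking data in that window count as a heavy day, although a telephone summary may stand in when TLFB data are unavailable.

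**The concern.** The definition and the table are two routes from the same reported drinks to the same daily total, and for 22-oz beer they disagree. The protocol does not say which one decides a day that falls at the cut-off.

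The endpoint is sensitive to this in principle because it allows no heavy day at all: one day on the wrong side of 4 or 5 can turn a responder into a non-responder. SDUs also feed the baseline percentage of heavy drinking days, which is a covariate in the primary model, and the drinking-quantity secondary endpoints.

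**Working it through.** **Inputs.** One SDU is 0.6 oz of pure alcohol, beer is 5% and malt liquor 7% (section 11.33 and Table 8). The cut-offs are 4 for women and 5 for men (section 9.1.1).

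**Is the definition itself consistent?** 0.6 fl oz x 29.57 mL x 0.789 g/mL = 14.0 g, with ethanol density assumed at 0.789 g/mL. This agrees with the 14 g in section 11.34, so the definition is not the outlier.

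**Table 8 against the definition.** SDU = ounces x strength / 0.6.

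| Entry | Formula | Result | Table 8 |
|---|---|---|---|
| Beer 12 oz | 12 x 0.05 / 0.6 | 1.00 | 1.0 |
| Beer 16 oz | 16 x 0.05 / 0.6 | 1.33 | 1.3 |
| Beer 22 oz | 22 x 0.05 / 0.6 | **1.83** | **2.0** |
| Beer 40 oz | 40 x 0.05 / 0.6 | 3.33 | 3.3 |
| Malt 12 oz | 12 x 0.07 / 0.6 | 1.40 | 1.4 |
| Malt 16 oz | 16 x 0.07 / 0.6 | 1.87 | 1.9 |
| Malt 22 oz | 22 x 0.07 / 0.6 | 2.57 | 2.6 |
| Malt 40 oz | 40 x 0.07 / 0.6 | 4.67 | 4.7 |

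The three wine entries and the 1.5-oz spirits entry also match. Over the whole table, 11 of 15 entries equal the formula to one decimal. Three of the four exceptions are the spirits containers (10.67, 16.67 and 39.33, printed as 11, 17 and 39). These are rounded to whole numbers and lie far above both cut-offs. The fourth is 22-oz beer, where 2.0 / 1.833 = 1.091, so the table is 9.1% high. To reach 2.0, the beer would have to be 2 x 0.6 / 22 = 5.45% strong, or the drink 22 x 0.05 / 2 = 0.55 oz. The protocol states neither.

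**Effect at the cut-offs if Table 8 values are summed.** All same-beverage combinations of one to five containers (430) were compared under both routes. Four change sides at 4 drinks and three at 5. These are counts of combinations, not frequencies of drinking days.

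From the 22-oz beer entry, all counted as heavy by the table but not by the definition:

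| Cut-off | Containers | Table 8 | Definition |
|---|---|---|---|
| 4 (women) | 2 x 22 oz | 4.0 | 44 x 0.05 / 0.6 = 3.67 |
| 4 (women) | 22 oz + 2 x 12 oz | 4.0 | 46 x 0.05 / 0.6 = 3.83 |
| 5 (men) | 2 x 22 oz + 12 oz | 5.0 | 56 x 0.05 / 0.6 = 4.67 |
| 5 (men) | 22 oz + 3 x 12 oz | 5.0 | 58 x 0.05 / 0.6 = 4.83 |

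From summing correctly rounded entries:

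| Cut-off | Containers | Table 8 | Definition |
|---|---|---|---|
| 4 (women) | 3 x 16 oz beer | 3.9 | 48 x 0.05 / 0.6 = 4.00 |
| 4 (women) | malt 12 oz + 22 oz | 4.0 | 34 x 0.07 / 0.6 = 3.97 |
| 5 (men) | 3 x 16 oz + 12 oz beer | 4.9 | 60 x 0.05 / 0.6 = 5.00 |

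Days that mix beverages were not enumerated, but the 22-oz entry acts there too. One 22-oz beer plus two 5-oz glasses of wine gives 4.0 by the table and 1.83 + 2.0 = 3.83 by the definition.

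**The case against.** **The calculator may already be right.** Its factors are not shown, and it may compute volume x strength / 0.6 directly. This stands: no misclassified day is demonstrated. Because the text names Table 8 as the SDU definition, use of the table is plausible, but it remains an assumption. The 22-oz cell would still need correcting.

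**Everything here is labelled approximate.** The drink size, the strengths and the table all carry that label, and subjects report amount and type rather than strength. This largely disposes of the three rounding cases. Three 16-oz beers total 4.0 only at exactly 5%; at 4.9% they total 48 x 0.049 / 0.6 = 3.92. The malt liquor pair reaches 4.0 at 2.4 / 34 = 7.06%. The 22-oz combinations are also sensitive to strength: 22 oz plus two 12 oz reaches 4.0 at 2.4 / 46 = 5.22%, and 22 oz plus three 12 oz reaches 5.0 at 3.0 / 58 = 5.17%. An unrounded formula therefore makes classification consistent, but it does not show that true heavy days are identified better. The label does not explain why one beer row departs from the one-decimal rounding that the other beer and malt liquor rows follow.

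**One day seldom decides a subject.** A changed day matters only if the subject has no other heavy day in Weeks 22-25 and is not already a failure through missing data. This stands, and the protocol gives no basis for estimating how many subjects that is.

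A reader might also infer that Table 8 as a whole conflicts with the definition, or that its 16-oz beer entry is wrong. Neither follows: 1.3 is the correct one-decimal value of 1.333, and 22-oz beer is the only beer or malt liquor row that fails.

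**Conclusion.** One cell of Table 8 is wrong by the protocol's own definition: 22-oz beer should read 1.8, not 2.0. The definition agrees with the 14 g equivalence, and every other beer and malt liquor row agrees with the definition.

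The consequence for the primary endpoint is conditional. If the calculator uses Table 8, the four 22-oz combinations count as heavy when the definition puts them below the cut-off. The three rounding combinations go in both directions and lie within the tolerance of the nominal strengths.

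A reader might infer that the treatment comparison is biased, or that power is reduced by a known amount. The document supports neither. The same conversion applies to both blinded arms, so the misclassification is unrelated to treatment. It would tend to dilute a difference rather than favour an arm, and its frequency cannot be derived. The planned 173 per group does not depend on Table 8. This is a minor point, worth correcting because the correction is so cheap.

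**What to change.** 1. Change the 22-oz beer entry in Table 8 to 1.8. Leave the 16-oz entry at 1.3.
2. Confirm which factors the TLFB spreadsheet uses. If they are the Table 8 values, set the calculator to ounces x nominal strength / 0.6, with no rounding before the daily total is compared with 4 or 5.
3. State that this unrounded total decides the day. Allow a small numerical tolerance at the cut-off, because totals such as three 16-oz beers fall exactly on 4.0 and should not depend on floating-point error.

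The cost is one table cell, a check or change of one formula, and one sentence. It should be settled before unblinding. If data have already been entered with Table 8 factors, the daily totals can be recomputed from the recorded amounts and beverage types, provided these were kept.

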11.34. World Health Organization Drinking Risk Categorical Scale

The WHO has developed a drinking risk categorical scale that can be used in a responder analysis approach to assess clinically relevant decreases in alcohol consumption (Aubin et al-2015). Two dichotomous endpoints will be analyzed: WHO 1-level and WHO 2-level decrease in alcohol consumption. The WHO 1- and 2-level decrease endpoints are the percentage of subjects experiencing at least 1- and 2-level decrease in WHO levels of alcohol consumption, respectively, from the level at baseline (the period including the 28 days before screening) to the level during the last 4 weeks of the maintenance phase (Study Weeks 22-25).

The WHO levels of average alcohol consumption per day are as follows:

	Males	Females
Low Risk	1 to 40g	1 to 20g
Medium Risk	41 to 60g	21 to 40g
High Risk	61 to 100g	41 to 60g
Very High Risk	101+g	61+g

where 14g = 1 SDU (WHO-2000). In computing the WHO alcohol consumption level, average drinks per day will be used, computed as the sum of all drinks in the 28 day period divided by the number of days with non-missing drinking data in that period. Abstinent subjects will be included in a separate "Abstinent" category. A subject must have at least 1 week of data during the last 4 weeks of the maintenance phase to be considered non-missing.

11.35. Urine Drug Screen

An FDA cleared, CLIA waived urine drug test card will be used to assess candidates for recent use of opioids, cocaine, amphetamines, methamphetamine, THC, buprenorphine, methadone or benzodiazepines. During screening subjects must be negative for all substances except THC and in special cases opioids. If positive for opioids but recent opiate use for acute pain is reported by the subject, then the subject can be re-screened. If positive for these drugs at other times during the study, the subject will not be removed from the study but should be asked about medication use and possibly re-evaluate their medical history for substance abuse.

11.36. Vital Signs

Vital signs to be assessed include sitting blood pressure and pulse rate (after sitting for at least 3 minutes).

12. Statistical Methods and Determination of Sample Size

12.1. Statistical and Analytical Plans

Complete details of the statistical analyses to be performed will be documented in a SAP, which will be completed prior to locking and unblinding the study data. This document will include more detail of analysis populations, summary strategies, and any amendments to the proposed analyses listed here, if necessary. Any changes to the SAP will be outlined in the final study report.

12.2. Statistical Hypotheses

Primary Efficacy Endpoint: It is hypothesized that HORIZANT Extended-Release Tablets, as compared to placebo will increase the PSNHDD during Study Weeks 22 to 25 (last 4 weeks of the maintenance period (where a heavy drinking day is defined as 5 or more drinks per drinking day for men, 4 or more drinks per drinking day for women). This hypothesis will be explored using other time periods in exploratory analyses.

Secondary Efficacy Endpoints:

Over the last 4 weeks of the maintenance period, it is hypothesized that the HORIZANT Extended-Release Tablets group, as compared to the placebo group, will:

- 1. Increase the percentage of subjects abstinent from alcohol (key secondary endpoint)
- 2. Increase the percentage of subjects with a WHO drinking risk category decrease of:
 - a. 1-level
 - b 2-levels
- 3. Increase the percentage of days abstinent per week
- 4. Decrease the percentage of heavy drinking days per week
- 5. Decease the weekly mean number of drinks per week
- 6. Decrease the weekly mean drinks per drinking day
- 7. Decrease the cigarettes smoked per week among smokers
- 8. Decrease the alcohol craving score (ACQ-SR-R) per visit
- 9. Decrease the alcohol related consequences (ImBIBe) score per visit
- 10. Decrease PSQI score
- 11. Decrease the BAI score
- 12. Decrease the BDI-II score

12.3. Analysis Populations

The study analysis populations will consist of the following:

Modified Intention-to-Treat (mITT) Analysis Set: The mITT set is defined as subjects randomized to participate in the study who took at least one dose of investigational product.

Evaluable Analysis Set: The evaluable analysis set is defined as those subjects randomized to the study who took at least 80% of the prescribed dose of tablets during the maintenance period (Weeks 2 - 25) and did not have a major protocol violation.

The primary and secondary efficacy endpoints will be analyzed on both the mITT and evaluable analysis sets. Exploratory analyses will be performed on the mITT analysis set, unless otherwise specified. Safety analyses will be conducted on the mITT analysis set.

12.4. Description of Statistical Methods

12.4.1. General Approach

For descriptive purposes, dichotomous and categorical variables will be presented as number of observations and percentages; continuous variables will be given as means, standard deviations (SD), median, minimum (min) and maximum (max). Statistical tests will be two-tailed at a 0.05 Type I error rate. P-values for the primary and secondary endpoints of < 0.05 will be considered statistically significant. Covariates will be pre-specified in the SAP. Endpoint data will also be screened for outliers and skewness. Appropriate non-parametric tests will be used to compare treatment groups on continuous baseline characteristics that are not normally distributed. Continuous endpoint data that are not normally distributed will be transformed. Cohen's d will be used to calculate the effect size for means and Cohen's h will be used to calculate the effect size for proportions. Odds ratios will be provided for all dichotomous outcomes and converted to Cohen's d where appropriate. Descriptive statistics – mean, SD, median, min and max – of all endpoint data will be provided for each assessment point or summarized at each week for drinking endpoints. All data will be presented in listings.

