The key secondary endpoint is the percentage of subjects abstinent during Weeks 22 through 25 on the mITT population. The analysis will be performed using a fully covaried logistic regression that includes treatment group, clinical site, pre-randomization drinking goal (abstinence versus not abstinent), and baseline percent days abstinent as covariates; however, fewer covariates may be included given a limited number of observed events. Subjects with any missing drinking data during Weeks 22 to 25 will be considered non-abstinent. Statistical significance will be evaluated if and only if the primary endpoint (PSNHDD) is statistically significant (p<0.05). The testing procedure utilizes serial gate keeping methodology (Dmitrienko and Tamhane 2009). If statistical significance for the primary endpoint of PSNHDD is met then the Wald statistic from the fully covaried logistic regression will be used to test treatment differences in the percentage of subjects abstinent with statistical significance identified with a two-tailed p-value below 0.05.

Analysis of the Supportive Secondary Endpoints:

Secondary endpoints will compare the HORIZANT Extended-Release Tablets group with the placebo group using mixed-effects models. Covariates for continuous secondary efficacy endpoints include the baseline equivalent of the endpoint, clinical site, treatment, time and the treatment by time interaction. Additional covariates for the secondary efficacy endpoints may include baseline characteristics with a theoretical and/or empirical basis for a relationship with a particular secondary endpoint. In general, every continuous secondary efficacy endpoint is analyzed using a repeated measures mixed effects model where subjects are random effects; factors and covariates are fixed effects. The overall least squares means and least square means for each time point along with the 95% confidence intervals will be presented for the untransformed endpoint only, while two-tailed p-values and Cohen's d will be presented for both the untransformed and transformed data. Inference and Cohen's d will be based upon the results using

appropriately transformed data. Percent subjects with a WHO 1-level decrease in alcohol consumption and a WHO 2-level decrease in alcohol consumption will be analyzed via a fully covaried logistic regression of the endpoint measured during the last 4 weeks of the maintenance period. No imputation will be used for the analysis of secondary endpoints.

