12.4.3. Secondary Efficacy Endpoints Analysis

12.4.3.1. Key Secondary Endpoint: Percentage of Subjects Abstinent from Alcohol

Percentage of subjects abstinent during Weeks 22 to 25 is the key secondary endpoint. Covariates for percentage of subjects abstinent will be the same as those for the primary endpoint PSNHDD as described in Section 9.4.2. Fewer covariates for the logistic regression may be used depending upon the number of events. If the number of events permits the inclusion of a baseline drinking covariate, the percentage of days abstinent will be used as the covariate for the percent subjects abstinent endpoint. The testing procedure utilizes the serial gate keeping methodology (Dmitrienko and Tamhane-2009). The key secondary endpoint can only be evaluated for statistical significance after the primary endpoint has been identified as statistically significant. In this situation, percentage of subjects abstinent will be evaluated using the Wald statistic from the logistic regression model at p<0.05 after PSNHDD is found to have p<0.05. If PSNHDD is not statistically significant at the 0.05 level then no significance testing of percentage of subjects abstinent will be performed. This analysis will be performed on mITT subjects with no imputation for missing data. However, if drinking data are missing by TLFB, but the subject reports any drinking during Weeks 22 to 25 using the Drinking Question eCRF, then the subject will be considered not abstinent. An analysis of percent subjects abstinent without imputation for missing data will be performed as an exploratory analysis.

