Results based on the primary analysis model and the model of the untransformed endpoint will be presented in tabular form. The overall least squares means and least square means for each time point along with the 95% confidence intervals will be presented for the untransformed endpoint only, while two-tailed p-values and Cohen's d will be presented for both the untransformed and transformed data. Inference and Cohen's d will be based upon the results using appropriately transformed data.

Analysis of the dichotomous secondary drinking endpoints, percent subjects with a WHO 1- and 2-level decrease in alcohol consumption (Aubin et al-2015), will be conducted via a fully covaried logistic regression model and contingency table. Covariates for the logistic regression model will be selected using a similar approach as that used for the primary endpoint PSNHDD as described in Section 9.4.2. Fewer covariates for the logistic regression may be used depending upon the number of observed events. No baseline drinking covariate will be employed for the endpoints, as these endpoints already adjust for baseline drinking in their calculation.

Covariates for both of these endpoints will be pre-specified in the SAP.

Analyses of supportive secondary endpoints with imputation for missing data will be performed as exploratory analyses.

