12.4.11. Multiple Comparison/Multiplicity

The primary endpoint and key secondary endpoint use the serial gate keeping methodology (Dmitrienko and Tamhane 2009) to maintain a family-wise Type I error of 0.05. This process requires an ordering of the hypotheses; namely, that the primary hypothesis for PSNHDD is evaluated first, followed conditionally by the key secondary hypothesis for percentage of subjects abstinent. This procedure requires that the primary hypothesis be rejected at p<0.05 then the hypothesis for the key secondary endpoint may be evaluated. If the primary hypothesis is not rejected then there is no test for the key secondary hypothesis. The serial gate keeping methodology indicates that if the primary hypothesis is rejected then the entire alpha (0.05, two-

sided) is available for the key secondary hypothesis. As such, the key secondary endpoint of percentage of subjects abstinent is evaluated at p<0.05 (two-sided) for statistical significance.

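### Section 12.4.1 labels every secondary p-value below 0.05 statistically significant, so 12 supportive hypotheses outside the gate get the label unadjusted, even after a failed primary

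*Protocol*

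**What the plan says.** The labelling rule is in Protocol Section 12.4.1 (General Approach): "P-values for the primary and secondary endpoints of < 0.05 will be considered statistically significant". It does not separate key from supportive secondary endpoints, does not refer to the gate, and names no analysis set.

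Multiplicity is handled in Section 12.4.11: "The primary endpoint and key secondary endpoint use the serial gate keeping methodology". The family-wise error of 0.05 claimed there is for those two endpoints. Section 12.4.3.1 spells out the consequence for abstinence: "If PSNHDD is not statistically significant at the 0.05 level then no significance testing of percentage of subjects abstinent will be performed". The synopsis says the same.

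Section 12.2 introduces the secondary hypotheses with "Over the last 4 weeks of the maintenance period, it is hypothesized that the HORIZANT Extended-Release Tablets group, as compared to the placebo group, will" and lists 12 numbered items. Item 1 is the key secondary endpoint. Item 2 has two parts (WHO risk decrease of one level and of two levels), and items 3 to 12 follow.

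For the continuous supportive endpoints, Section 12.4.3.2 provides two-tailed p-values and adds that "Inference and Cohen's d will be based upon the results using appropriately transformed data". Section 12.3 states that "The primary and secondary efficacy endpoints will be analyzed on both the mITT and evaluable analysis sets".

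**The concern.** The label in Section 12.4.1 reaches further than the error control in Section 12.4.11. The 12 supportive hypotheses receive the same words as the controlled tests, at an unadjusted 0.05, and nothing makes this depend on the primary result.

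This turns the hierarchy round. After a failed primary, the higher-ranked secondary endpoint may not be tested at all. Percent days abstinent, drinks per week or the craving score may still be reported as statistically significant. That is the situation in which a sponsor most wants a positive statement and in which a gate is meant to prevent one.

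The rule also covers p-values from the evaluable set, which is selected on tablet-taking after randomization (at least 80% of the prescribed dose).

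**Working it through.** **Count of hypotheses outside the gate.** Section 12.2: 2 (items 2a and 2b) + 10 (items 3 to 12) = 12.

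**The plan's own figure.** With the primary tested at two-sided 0.05 and abstinence tested at 0.05 only if the primary is rejected, the family-wise error for the pair is at most 0.05. Section 12.4.11 is correct for the two endpoints it names. The protocol states no error rate for the other 12.

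**Is there text that overrides the rule?**
- Key secondary endpoint: yes. The synopsis and Sections 12.4.3.1 and 12.4.11 are specific and would prevail. Only a cross-reference is missing.
- Supportive endpoints: none. Sections 12.4.3.2 and 12.4.11 contain no gate, no adjustment and no statement that these p-values are nominal or descriptive.

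**Size under no drug effect, mITT set only.** The protocol gives no correlations between endpoints, so every correlation below is an assumption. Let *c* = 1.96, with test statistics signed so that positive means benefit.

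*Common correlation ρ across the primary and the 12 supportive tests.* Given a shared normal factor *a*, define
- *q(a)* = Φ[(c − √ρ·a)/√(1−ρ)] − Φ[(−c − √ρ·a)/√(1−ρ)], the chance that one test is not significant;
- *u(a)* = Φ[(c − √ρ·a)/√(1−ρ)], the chance that one test is not significant in favour of drug.

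Averaging over *a*:
- any label = E[1 − q¹²];
- any label and primary p ≥ 0.05 = E[q(1 − q¹²)];
- label favouring drug = E[1 − u¹²];
- label favouring drug and primary p ≥ 0.05 = E[q(1 − u¹²)].

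| ρ | Favouring drug, primary failed | Favouring drug | Any label, primary failed | Any label |
|---|---|---|---|---|
| 0.3 | 0.188 | 0.202 | 0.368 | 0.397 |
| 0.5 | 0.142 | 0.160 | 0.284 | 0.319 |
| 0.7 | 0.095 | 0.116 | 0.191 | 0.232 |
| 0.9 | 0.044 | 0.067 | 0.088 | 0.135 |

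*Block correlation.* Items 2 to 6 come from the same Timeline Followback record as the primary. Items 2a and 2b are nested, because Section 11.34 defines them as the "percentage of subjects experiencing at least 1- and 2-level decrease in WHO levels of alcohol consumption". A block structure is therefore more realistic than one common ρ. The blocks are the primary with 2a, 2b and 3-6, and items 7-12. Each row is a simulation of 1,000,000 draws.

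| Within drinking block | Within items 7-12 | Across | Favouring drug, primary failed | Any label, primary failed | Any label |
|---|---|---|---|---|---|
| 0.7 | 0.3 | 0.2 | 0.163 | 0.318 | 0.358 |
| 0.8 | 0.3 | 0.2 | 0.152 | 0.297 | 0.340 |
| 0.9 | 0.3 | 0.2 | 0.138 | 0.272 | 0.318 |
| 0.7 | 0.5 | 0.3 | 0.143 | 0.284 | 0.323 |
| 0.9 | 0.5 | 0.3 | 0.120 | 0.237 | 0.283 |

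*Upper reference.* Independence would give 1 − 0.95¹² = 0.460 in either direction and 1 − 0.975¹² = 0.262 favouring drug. These endpoints are plainly not independent.

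Repeating the tests in the evaluable set would add further opportunities. They are not counted here.

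**The case against.** Leaving supportive endpoints unadjusted is an accepted choice, and the protocol never claims that they are controlled. Its family-wise statement is confined to the two gated endpoints and is correct. The sentence before the rule in Section 12.4.1 sets a two-tailed 0.05 level, so the rule can be read as a per-test threshold. On that reading it does not contradict Section 12.4.11, and each single test is still held at 5%. The objectives already separate key from supportive, which tells a reader that the latter are not confirmatory. The remark about inference in Section 12.4.3.2 mainly settles whether the transformed or the untransformed model governs, so it is weak evidence of confirmatory intent. The analysis plan might also add a footnote.

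Much of this stands as a limit on weight. It is the family-wise rate that is uncontrolled, not the per-test rate, and the inference sentence should not carry much. The probabilities that matter most are those favouring drug after a failed primary, which are smaller than the either-direction figures.

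It does not remove the fault. The word supportive has no stated consequence for the significance label, and Section 12.4.1 is an explicit rule rather than a gap left for later. A restriction in the analysis plan would conflict with that rule unless the rule is changed. The point asks for no adjustment, only that an uncontrolled result not carry the same label as a controlled one.

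**Conclusion.** The concern holds for the 12 supportive hypotheses. As written, the plan allows statistically significant supportive findings to be reported after a failed primary, with no control of the family-wise error.

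Under no drug effect, in the mITT set, a favourable label alongside a failed primary has a probability of about 12-16% under the block assumptions and 4-19% under common correlations of 0.9 down to 0.3. A label in either direction, regardless of the primary, has a probability of 28-36% and 13-40% respectively. The ranges depend on the assumed correlations. Only the narrowest measure at the highest correlation (0.044) falls below 5%.

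For the key secondary endpoint the omission is only a missing cross-reference. The primary test, the gated key secondary test, power and sample size are sound on this point. The correction should be made, but it concerns what may be claimed, not how the data are analysed.

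**What to change.** Replace the sentence in Section 12.4.1 with:

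> Statistical significance will be declared only for the primary endpoint (mITT, p<0.05) and, subject to the gate in Section 12.4.11, for the key secondary endpoint (mITT, p<0.05). P-values for the supportive secondary endpoints, and all p-values from the evaluable set, will be reported as nominal.

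This also supplies the missing cross-reference to the gate. It changes no data, model or sample size. The only cost is weaker language for the supportive endpoints.
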